## 6. Statistics

To the case series will be applied a descriptive statistic.

For the exploratory objectives, positive and negative expression of CXCR4 and CXCL12 (nuclear and cytoplasmatic) will be correlated with ES and OS.

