## **1. Background**

Treatment of osteosarcoma has evolved in the last 40 years: with the introduction of neo-adjuvant chemotherapy, 5-year survival rates for patients affected by high-grade osteosarcoma have improved from 15% to more than 70%.

To date, many osteosarcomas are cured by multiagent chemotherapy and surgery, but a significant number still relapse: after treatment of the primary osteosarcoma, 40% to 50% of patients will develop local relapse (LR), distant metastases (DM) or both.

Few analyses in literature report on locally recurrent disease as it remains uncommon, with LR rate ranging from 4% to 10%. Prognosis of patients experiencing LR is generally considered poor, however most data available do not provide sufficient details. DM are such an overriding determinant of survival, and LR is so infrequent, that it is difficult to study local recurrence as an independent variable.

Also, in case of LR, while the importance of achieving a second surgical complete remission is well known (CR2), the role of second line chemotherapy is under discussion, with a mono-institutional experience showing no advantage in of chemotherapy after local relapse. Several molecules and their receptors are known to be involved in migration and invasiveness of tumour cells including CXCL12 (SDF-1) which is the ligand of Receptor-4 (CXCR4). The binding of CXCL12 to CXCR4 it is known to activate downstream cascades involving many signalling pathways, such as JAK/STAT, PI3K/Akt, MAPK, JNK which are key in cell migration. The expression of CXCR4 is low or absent in normal cells, while it is elevated in tumor cells. There are preclinical evidences that CXCR4 has an important role on tumor progression in sarcoma. Also, nuclear expression of CXCR4 and IGF-1R negatively influences survival in patients with localized soft tissue sarcoma.

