## **2. Objectives**

Aim of this study is to analyse the modalities of diagnosis (symptoms versus planned radiology) of LR for high-grade osteosarcoma patients, pattern of recurrence, treatment of LR and factors influencing post-LR survival (PLRS) on the role of second line chemotherapy, margins, Local relapse-free interval (LRFI) (“early LR” recurrences with an LRFI ranging between 1 and 24 months, and “late LR” as those having an LRFI longer than 24 months).

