### **Secondary Objectives**

- analyse the modalities of diagnosis of LR in high-grade osteosarcoma
- pattern of recurrence
- treatment of LR
- Prognostic factors for PLRS (second line chemotherapy, surgical margins, surgical complete remission after LR (CR2), type of surgery)

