### **Exploratory Objectives**

Assessment of CXCR4 and CXCL12 (SDF-1) expression classified as nuclear, cytoplasmatic, and both in primary tumor, LR and DM

- Comparison of CXCR4 and CXCL12 (SDF-1) expression in the LR samples between the groups of patients with isolated LR and those presenting with LR and DM
- Comparison of CXCR4 and CXCL12 (SDF-1) expression on primary tumor in 3 group of patients:
  - 1- patients with non LR, nor DM (archival series from Rizzoli database)
  - 2- patients with isolated LR
  - 3- patients with LR + DM

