#### **4. Prospective observational analysis and data collection**

Clinical data will be retrieved by patient charts.

A protocol-specific CRF reporting the results of the review will be provided.

Data from all patients diagnosed with OS will be prospectively entered in this platform.

Each patient will be provided with an informational leaflet for his/her general practitioner and asked to sign an informed consent prior to data entry.

The following information will be recorded in the database:

- Demographics – patient name, DOB, gender, date of first consultation, data of diagnosis
- Data on primary tumor – size, site, evidence of multifocality
- Data on histological diagnosis – morphology (classical type, proximal type, mixed), mitotic count, depth
- Data on staging at diagnosis – evidence of lymph-nodal and/or distant metastases
- Data on treatment of primary tumor – surgery, radiotherapy, chemotherapy
- Data on recurrence – type of recurrence, site, date
- Data on treatment of local relapse – surgery, radiotherapy, chemotherapy
- Data on treatment of metastatic disease – pulmonary metastasectomy, radiotherapy
- Data on chemotherapy for metastatic disease – line, regimen, number of cycles, best response, duration of response
- Patient status at last follow-up (dead of disease, DOD, alive with disease, AWD, nonevidence of disease, NED)

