##### **Inclusion criteria**

- Patients who experienced LR as first event of recurrence after treatment for localized high-grade osteosarcoma of bone, including cases with synchronous lung metastases
- Adequate patient compliance to follow-up visits
- Written informed consent prior to any study-specific analysis and/or data collection
- No age limits

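### Section 6 names only a descriptive statistic, which does not fit the objective of prognostic factors for post-LR survival, two of which arise only after LR

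*Protocol*

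**What the plan says.** Protocol section 2 sets the aim as including "factors influencing post-LR survival (PLRS) on the role of second line chemotherapy, margins, Local relapse-free interval (LRFI"). The Secondary Objectives list "Prognostic factors for PLRS (second line chemotherapy, surgical margins, surgical complete remission after LR (CR2), type of surgery"). The Background gives the motive: after local relapse, "the role of second line chemotherapy is under discussion".

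Section 6 answers with one sentence for the clinical objectives: "To the case series will be applied a descriptive statistic". Its only other sentence concerns the exploratory markers.

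On distant metastases, the Background says "DM are such an overriding determinant of survival". The prospective inclusion criteria admit LR as first event, "including cases with synchronous lung metastases", and the exploratory marker comparison is made "between the groups of patients with isolated LR and those presenting with LR and DM". DM at LR is in neither list of factors for PLRS in section 2.

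On data, the prospective list in section 4 gives "Data on treatment of local relapse – surgery, radiotherapy, chemotherapy" and has no CR2 item. The retrospective list in section 5 has a CR2 date and DM status at LR, but gives treatment after LR only by type.

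**The concern.** A descriptive statistic serves overall PLRS, mode of diagnosis, pattern of recurrence and treatment of LR. It does not serve a question about which factors influence PLRS. The protocol is not silent here: it names a method, and the method does not fit one of its own objectives.

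The gap matters most for second-line chemotherapy and CR2. Neither is known on the date of LR, when PLRS starts. The simplest descriptive display would split patients by whether they ever had the factor. A patient must live long enough to receive chemotherapy or reach CR2, so patients who die early count as never. This is immortal-time bias, and it favours the factor even when the factor does nothing. DM at LR adds a second distortion if it affects both survival and the chance of receiving the factor. A reader of such a display could not tell bias from effect, on a question that the Background presents as open.

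**Working it through.** **No figure to reproduce.** The protocol gives no expected PLRS, uptake, event count or effect size. Planned numbers are about 100 retrospective and 50 prospective patients, 150 in all. Every input below is an assumption, used only to show how large the hazard could be.

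**Step 1: immortal time alone, no true effect.** Assume exponential PLRS with rate L = ln 2 / median. A share p of patients is destined for the factor, at a time uniform over the first m months after LR, and receives it only if still alive.

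- Probability that a destined patient lives to receive it: e = (1 − exp(−Lm)) / (Lm).
- 24-month PLRS in the ever group: S(24)/e.
- 24-month PLRS in the never group: (1 − p)·S(24) / (1 − p·e).

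Example: median 24 months gives L = 0.0289 and S(24) = 50% for everyone. With m = 12, e = 0.845. Ever = 0.50/0.845 = 59%. Never at p = 0.5 is 0.25/(1 − 0.4226) = 43%. Never at p = 0.8 is 0.10/(1 − 0.6761) = 31%.

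| Median 24 months | m = 3 | m = 6 | m = 12 |
|---|---|---|---|
| p = 50%: ever vs never | 52 vs 48% | 55 vs 46% | 59 vs 43% |
| p = 80%: ever vs never | 52 vs 43% | 55 vs 38% | 59 vs 31% |

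Over medians of 12, 24 and 36 months the false gap runs from about 4 points (median 36, p = 50%, m = 3) to about 28 points (median 24, p = 80%, m = 12).

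A separate simulation used 150 patients, median 12 or 24 months, 50% uptake and mean delays of 1, 3 or 6 months. Average hazard ratios were 0.65 to 0.91 with ever/never coding and 0.97 to 1.01 with time-dependent coding, where the true value is 1.

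**Step 2: adding DM at LR.** Assume 30% have DM, with a death hazard ratio of 2 to 3 against no DM, and a median of 24 months without DM. Simulated with no true effect:

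- CR2 in 40% with DM and 80% without: crude false gap +15 to +33 points (hazard ratio 0.42 to 0.67).
- Chemotherapy in 80% with DM and 40% without: crude gap −6 to +11 points (0.79 to 1.12). Here the two biases pull in opposite directions.

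| Hazard ratio (true value 1) | Chemotherapy | CR2 |
|---|---|---|
| Ever/never, stratified by DM | 0.58–0.85 | 0.54–0.83 |
| Time-dependent, DM ignored | 1.20–1.31 | 0.72–0.82 |
| Time-dependent and stratified by DM | 0.99–1.01 | 0.99–1.01 |

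Neither correction is enough alone.

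**Step 3: what remains.** One unmeasured factor (30% prevalence, death hazard ratio 1.5 to 3, uptake multiplied by 0.4 to 0.7) still leaves 0.75 to 0.93 for CR2 and 0.81 to 0.95 for chemotherapy after both corrections. Confounding by indication is not removed.

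**Step 4: the data lists.** A time-dependent or landmark analysis needs the CR2 date and the start date of post-LR chemotherapy. The CR2 date is in the retrospective list and absent from the prospective one. Neither list explicitly names the start date of post-LR chemotherapy.

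**The case against.** The strongest reply is that section 6 does not rule out a model, that a plot of PLRS by factor is itself descriptive, and that time-dependent covariates, landmarks and adjustment sets commonly belong in a statistical analysis plan. Part of this stands: model details can be left to such a plan. The mismatch does not go away, because the one method named for the clinical objectives cannot soundly answer one of them.

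Four stronger readings are tempting and not supported:

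- *The plan contains a biased comparison.* No passage plans an ever/never split. The figures show what could follow from one, on assumed inputs.
- *Chemotherapy will look falsely beneficial.* The crude gap can go either way, depending on who is treated.
- *The dates will not be collected.* The lists are by category, both cohorts draw on patient charts, and the case report form is not shown and may hold them. Reading the retrospective items on chemotherapy timing and surgery date as primary treatment only is an inference from word order. In the prospective cohort, DM at LR may be derivable from recurrence type and date.
- *Margins and type of surgery also arise after LR.* The Secondary Objectives do not say which surgery is meant, and section 5 lists margins under both primary treatment and LR.

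Omitting DM at LR from the factor lists is also softened: it is collected retrospectively, and pattern of recurrence is itself an objective.

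**Conclusion.** The concern holds as a mismatch between section 6 and section 2, and should be fixed. Followed as written, the plan cannot soundly answer the objective on prognostic factors for PLRS, and it has no stated safeguard for the two factors that arise after LR. The possible size, about 4 to 28 points of false difference in 24-month PLRS from immortal time alone, depends wholly on assumed survival, uptake and timing, and on a comparison that the protocol does not state. DM at LR should be among the factors, given the weight that the Background puts on it. The gap in the data lists is one of explicitness. Its firmest part is that CR2 appears in the retrospective list and not in the prospective one. Confidence is medium.

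**What to change.** In section 6, state that PLRS is described by Kaplan-Meier from the LR date. State that second-line chemotherapy and CR2 are assessed as time-dependent covariates in a Cox model, or by landmark, stratified by or adjusted for DM at LR. Report the results as associations, because confounding by indication remains. Add DM at LR to the factors in the Secondary Objectives.

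In the data lists, add the CR2 date to section 4 and make the start date of post-LR chemotherapy explicit in sections 4 and 5. Say whether surgical margins and type of surgery in the Secondary Objectives mean the primary or the LR surgery. If LR surgery, compare them among operated patients from the date of that surgery, and record that date.

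The alternative is to limit section 2 to description and make no claim about the role of chemotherapy or CR2. That costs only wording.

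The first route costs a few sentences, a few data fields and modest analysis work. Some dates may be hard to find in charts going back to 1980, and a landmark excludes early deaths.

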## 7. Enrolment procedures

Patients considered eligible and who have provided a written informed consent will be

included into the study and their material will be used for the purpose of this research according to the protocol and to the informed consent provided.

For the retrospective analysis, the investigator will extract from Institute database the list of potential eligible patients for whom the tumor material is available. After the verification of the presence of the study enrollment criteria, the patient will be included in the study.

Due to the high incidence of mortality of the disease under investigation, it would be possible that some eligible subjects will be deceased

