## **3. STUDY DESIGN**

This is a multicenter retrospective and prospective study that will analyze all cases with of

diagnosis of LR in high-grade osteosarcoma from 01 January 1980 and all new cases referring to each participant site.

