#### **4.1 Study population**

We plan to include approximately 50 patients in 36 months.

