#### **5. Retrospective observational analysis and data collection**

Together with the prospective observational study, a retrospective analysis including all the cases with a histological diagnosis of localized high-grade osteosarcoma who experienced LR as first event of recurrence after treatment from 01 Jan 1980 to 31 Dec 2021 will be performed.

The data will be extracted retrospectively from prospectively maintained institutional database and will be checked through a revision of patient records.

The following data will be collected:

- demographics (gender, date of birth, age at diagnosis),

- disease characteristics (morphological subtype, dimension, primary site),
- treatment received (date of surgery, surgical margins, radiation therapy, timing of radiation therapy, chemotherapy, timing of chemotherapy, type of regimen used, best response according to RECIST 1.1)
- date of LR, modality of LR diagnosis, clinical suspect or imaging, presence, or absence of DM at LR diagnosis, type of treatment after LR, date of surgical complete remission after LR (CR2), surgical margins
- outcome (recurrence type and timing, patient status at last follow-up)

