## 5.1 Study population

Through the collaboration of the joining institutions, we plan to include approximately 100 patients

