### Inclusion criteria

- Male and female patients treated for localized high-grade osteosarcoma from 01 Jan 1980 to 31 Dec 2021.
- Clinical Information available
- No age limits

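### Section 7 builds the retrospective list from patients with available tumour material, a condition that Sections 3 and 5 do not state and the Section 5.1 criteria do not contain

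*Protocol*

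**What the plan says.** Section 7 (Enrolment procedures) sets out the retrospective route in two consecutive sentences. First, "For the retrospective analysis, the investigator will extract from Institute database the list of potential eligible patients for whom the tumor material is available". Then, "After the verification of the presence of the study enrollment criteria, the patient will be included in the study".

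Other sections describe a cohort with no tissue condition:

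- Section 3: "This is a multicenter retrospective and prospective study that will analyze all cases with of" LR in high-grade osteosarcoma since 1 January 1980 (the sentence runs on, with a stray word).
- Section 5: "a retrospective analysis including all the cases with a histological diagnosis of localized high-grade osteosarcoma who experienced LR as first event of recurrence", for the years 1980 to 2021.
- Section 5, on the data source: "The data will be extracted retrospectively from prospectively maintained institutional database and will be checked through a revision of patient records".
- Section 5.1, retrospective criteria: the only availability requirement is "Clinical Information available". The exclusions concern the timing of LR relative to metastatic disease, and metastases at presentation. Lack of tissue is not among them.

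The optional sub-study paragraph in Section 4 and Section 11 deal with tissue. Both are limited to cases with FFPE tissue and depend on funding.

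On size, Section 5.1 states: "Through the collaboration of the joining institutions, we plan to include approximately 100 patients". Section 4.1, for the prospective part, states: "We plan to include approximately 50 patients in 36 months".

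**The concern.** The primary objective in Section 2 is PLRS. It can be obtained from dates and status in the database and charts, so stored tissue is irrelevant to it. Yet Section 7, followed literally, lets tissue availability decide who is screened. A sub-study that may never be funded would then shape the main cohort.

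Two things are at stake. First, in a multicentre series, a site working from Section 7 and a site working from Sections 5 and 5.1 would submit different case lists under the same protocol. Second, tissue availability may not be unrelated to outcome. Section 7 does not say whether primary, LR or metastatic tissue is meant. If LR tissue is meant, availability could depend on whether the relapse was operated on. Type of surgery, margins and second surgical remission (CR2) are prognostic factors listed in Section 2, so selection could act on the variables under study. A descriptive analysis gives no protection, because it is only as representative as its case list. Any PLRS estimate that pooled the two parts would carry the same selection.

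**Working it through.** **1. Order of steps in Section 7.** List patients with material, verify the enrolment criteria, include in the study. A patient without material is not listed and so is not checked. Section 7 offers no second way in for retrospective patients.

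**2. The same patient under each section.** Take a patient treated for localised high-grade osteosarcoma in the period, with LR as first event, full clinical records and no stored tissue.

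| Place | Outcome for this patient |
|---|---|
| Section 3 | Analysed |
| Section 5 | Included |
| Section 5.1 criteria | Eligible (no tissue item) |
| Section 7 | Not listed, so not included |

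Section 5.1 supports the point only by its silence on tissue. Its criteria do not mention LR; the all-cases wording is in Sections 3 and 5.

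**3. Share of the study under the clause.** Inputs: about 100 retrospective (Section 5.1) and about 50 prospective (Section 4.1). The protocol prints no total; the sum is 100 + 50 = 150.

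- 100 / 150 = 66.7%.

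This is the share whose entry is governed by the clause, not the share lost. The prospective criteria in Section 4.1 have no tissue item, so those 50 are not affected.

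**4. Possible loss.** Let q be the proportion of retrospective LR cases without tissue. The protocol gives no value. As an assumption, take q = 0.10 to 0.30.

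- If the planned 100 counts all LR cases, the number left out is 100 × q = 10 to 30. That leaves 90 to 70 retrospective patients and 140 to 120 in total. As a share of 150: 10/150 = 6.7% and 30/150 = 20.0%.
- If the 100 counts only cases with tissue, the number eligible is 100 / (1 − q): 100/0.90 = 111 and 100/0.70 = 143. Never listed: about 11 to 43.

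Archives reaching back to 1980 could be thinner than that. On the first reading, q = 0.50 would leave 50 retrospective patients (100 in total), and q = 0.70 would leave 30 (80 in total).

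**5. Effect on precision (illustration).** For a survival proportion near 50%, ignoring censoring, the 95% half-width is 1.96 × √(0.25/n): 9.8 percentage points at n = 100, 10.3 at n = 90 and 11.7 at n = 70. Over the 10% to 30% range the loss of precision is modest. Selection is the larger worry.

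**6. Bias.** The error in retrospective PLRS at a fixed time would be q × d, where d is the survival difference between patients with and without tissue. The protocol gives neither q nor d, so no figure and no direction can be stated.

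**The case against.** The best counter-argument is that the clause is leftover sub-study wording. The sentence before it in Section 7 speaks of how patients' material will be used. The enrolment criteria it points to contain no tissue item. Nor does Section 7 say outright that a patient without material is ineligible. On that reading the main cohort is still all LR cases.

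This may well be how the clause arose, but it does not remove the conflict. The sentence opens by applying to the retrospective analysis, and the next one ends with inclusion in the study. Where the protocol means the sub-study, it says so and adds the funding condition; Section 7 does neither.

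Three further objections stand in part:

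- **Size.** The assumed 10% to 30% has no basis in the protocol, so the counts derived from it only show scale.
- **Bias path.** The link to surgery and CR2 holds only if LR tissue is meant. Section 5 requires a histological diagnosis, so primary tissue existed at some time. If primary tissue is meant, the link to relapse surgery does not follow, though archive retention could still vary.
- **Consequences.** The planned analysis is descriptive with no stated power, so no test is shown to be harmed. That sites would in fact diverge is a risk rather than a demonstrated event.

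**Conclusion.** The concern holds: Section 7 contradicts Sections 3 and 5 and adds a condition that is absent from the Section 5.1 criteria. This is an enrolment rule stated wrongly, not a detail that could be left to a SAP, and later analysis cannot recover patients who were never listed. It governs about 100 of about 150 planned patients (67%) and does not touch entry to the prospective part. Confidence is high for the contradiction. The number lost rests entirely on the assumed availability rate, and no size or direction of bias in PLRS is claimed. It should be fixed.

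**What to change.** In Section 7, remove the tumour-material condition from the main retrospective listing, so that every case meeting Section 5 and the Section 5.1 criteria is listed and checked. Put the condition in the optional sub-study paragraph. That paragraph already names primary, LR and metastatic tissue; it should add which specimen, or combination, a patient needs to count as having material. It would help to record tissue availability for each specimen on the CRF and to report how many eligible patients have it, so that readers can judge the sub-study's selection.

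If tissue is truly meant as a condition for the main cohort, list it in Section 5.1 with the specimen named, and qualify the all-cases wording in Sections 3 and 5 to match.

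The cost is a short protocol amendment and some extra chart abstraction for patients without tissue. No new procedures are needed.
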